7.7.8 Tanner Staging (Sexual Maturity Ratings)

Tanner staging is widely used to assess adolescents' physical development during puberty in 5 stages (from preadolescent to adult). Also known as Sexual Maturity Ratings (SMRs), Tanner stages are a way of assessing the degree of maturation of secondary sexual characteristics (see [Appendix D](#) for guidance). The developmental stages of the adolescent's sexual characteristics will be rated and recorded separately (ie, one stage for pubic hair and one for breasts in females, one stage for pubic hair and

one for genitals in males), because these characteristics may differ in their degree of maturity.

8. WITHDRAWAL FROM TREATMENT, PROCEDURES, AND STUDY

8.1 Subjects' Decision to Withdraw

Subjects have the right to withdraw from the study at any time and for any reason without prejudice to their future medical care by the physician or at the institution.

Subjects (or a legally acceptable representative) can decline to continue receiving investigational product and/or other protocol-required therapies or procedures at any time during the study but continue participation in the study. If this occurs, the investigator is to discuss with the subject the appropriate processes for discontinuation from investigational product or other protocol-required therapies and must discuss with the subject the options for continuation of the Schedule of Assessments (Table 2) and collection of data, including endpoints and adverse events. The investigator must document the change to the Schedule of Assessments (Table 2) and the level of follow-up that is agreed to by the subject (eg, in person, by telephone/mail, through family/friends, in correspondence/communication with other physicians, from review of the medical records).

Withdrawal of consent for a study means that the subject does not wish to receive further protocol-required therapies or procedures, and the subject does not wish to or is unable to continue further study participation. Subject data up to withdrawal of consent will be included in the analysis of the study, and where permitted, publically available data can be included after withdrawal of consent. The investigator is to discuss with the subject appropriate procedures for withdrawal from the study. The investigator should ask the subject's consent to perform the procedures listed under the final study visit.

8.2 Investigator or Sponsor Decision to Withdraw or Terminate Subjects' Participation Prior to Study Completion

The investigator and/or sponsor can decide to withdraw a subject(s) from investigational product and/or other protocol-required therapies, protocol procedures, or the study as a whole at any time prior to study completion.

Subjects may be eligible for continued treatment with Amgen investigational product(s) and/or other protocol-required therapies by a separate protocol or as provided for by the local country's regulatory mechanism, based on parameters consistent with

[Section 12.1](#).

8.3 Reasons for Removal From Treatment or Study

8.3.1 Reasons for Removal From Treatment

Reasons for removal from protocol-required investigational product or procedural assessments include any of the following:

- subject request
- safety concern (eg, due to an adverse event, failure to follow contraception, pregnancy, breast feeding, and/or protocol requirements)
- withdrawal of consent from study
- death
- lost to follow-up
- decision by Sponsor (other than subject request, safety concern, lost to follow-up)

8.3.2 Reasons for Removal From Study

Reasons for removal of a subject from the study are:

- withdrawal of consent from study
- death
- lost to follow-up
- decision by sponsor

9. SAFETY DATA COLLECTION, RECORDING, AND REPORTING

9.1 Definition of Safety Events

9.1.1 Adverse Events

An adverse event is defined as any untoward medical occurrence in a clinical trial subject. The event does not necessarily have a causal relationship with study treatment. The investigator is responsible for ensuring that any adverse events observed by the investigator or reported by the subject are recorded in the subject's medical record.

The definition of adverse events includes worsening of a pre-existing medical condition. Worsening indicates that the pre-existing medical condition or underlying disease (eg, diabetes, migraine headaches, gout) has increased in severity, frequency, and/or duration more than would be expected, and/or has an association with a significantly worse outcome than expected. A pre-existing condition that has not worsened more than anticipated (ie, more than usual fluctuation of disease) during the study or involves an intervention such as elective cosmetic surgery or a medical procedure while on study, is not considered an adverse event.

An adverse device effect is any adverse event related to the use of a medical device. Adverse device effects include adverse events resulting from insufficient or inadequate instructions for use, adverse events resulting from any malfunction of the device, or adverse events resulting from use error or from intentional misuse of the device.

The investigator's clinical judgment is used to determine whether a subject is to be removed from treatment due to an adverse event. In the event a subject, or subject's legally acceptable representative requests to withdraw from protocol-required therapies or the study due to an adverse event, refer to [Section 8.1](#) for additional instructions on the procedures recommended for safe withdrawal from protocol-required therapies or the study.

9.1.2 Serious Adverse Events

A serious adverse event is defined as an adverse event that meets at least 1 of the following serious criteria:

- fatal
- life threatening (places the subject at immediate risk of death)
- requires in-patient hospitalization or prolongation of existing hospitalization
- results in persistent or significant disability/incapacity
- congenital anomaly/birth defect
- other medically important serious event

An adverse event would meet the criterion of "requires hospitalization", if the event necessitated an admission to a health care facility (eg, overnight stay).

If an investigator considers an event to be clinically important, but it does not meet any of the serious criteria, the event could be classified as a serious adverse event under the criterion of "other medically important serious event". Examples of such events could include allergic bronchospasm, convulsions, blood dyscrasias, DILI (see [Appendix A](#) for drug-induced liver injury reporting criteria), or events that necessitate an emergency room visit, outpatient surgery, or urgent intervention.

9.2 Safety Event Reporting Procedures

9.2.1 Adverse Events

9.2.1.1 Reporting Procedures for All Adverse Events (Serious or Non-serious Adverse Events)

Refer to [Sections 9.2.1.2](#) and [9.2.1.3](#) for additional information regarding the reporting of serious adverse events.

For subjects enrolling in Study 20120124 after completion of Study 20120123 (HeFH subjects) the investigator is responsible for ensuring that all adverse events and all adverse device effects observed by the investigator or reported by the subject that occur after the first dose of investigational product/study treatment/protocol-required therapies through the end of Study 20120124 are reported using the Event CRF.

For subjects not rolling over from Study 20120123 (HoFH subjects), the investigator is responsible for ensuring that all adverse events possibly related to study procedures, adverse device effects, and serious adverse events are reported from signing of the ICF. All other adverse events are reported that occur after enrollment. The investigator is responsible for ensuring that all adverse events observed by the investigator or reported by the subject that occur from signing of the ICF or that occur after enrollment through the end of Study 20120124 are reported using the Event CRF.

The investigator must assign the following adverse event attributes:

- adverse event diagnosis or syndrome(s), if known (if not known, signs or symptoms),
- dates of onset and resolution (if resolved),
- severity,
- assessment of relatedness to investigational product (evolocumab and/or the device[s]: the prefilled AI/Pen or AMD), or other protocol-required therapies, protocol-required procedure or activity, and
- action taken.

The adverse event grading scale used will be the National Cancer Institute (NCI) Common Terminology Criteria for Adverse Events (CTCAE). The grading scale used in this study is referenced in [Appendix A](#).

If the severity of an adverse event worsens from the date of onset to the date of resolution, record a single event for each increased level of severity on the Adverse Event Summary CRF.

The investigator must assess whether the adverse event is possibly related to IMP (evolocumab). This relationship is indicated by a “yes” or “no” response to the question: Is there a reasonable possibility that the event may have been caused by evolocumab (investigational medicinal product)? The investigator must assess whether the adverse event is possibly related to the prefilled AI/Pen or the AMD (investigational device(s) used to administer evolocumab). The relationship is indicated by a “yes” or “no” response to the question: Is there a reasonable possibility that the event may have been

caused by the investigational device? Relatedness means that there are facts or reasons to support a relationship between IP and the event.

The investigator must assess whether the adverse event is possibly related to any study-mandated activity (eg, administration of investigational product, protocol-required therapies, device(s) and/or procedure (including any screening procedure(s))). This relationship is indicated by a “yes” or “no” response to the question: “Is there a reasonable possibility that the event may have been caused by a study activity (eg, administration of investigational product, protocol-required therapies, device(s)), and/or procedure”?

The investigator is responsible for reviewing laboratory test results and determining whether an abnormal value in an individual study subject represents a clinically significant change from the subject’s baseline values. In general, abnormal laboratory findings without clinical significance (based on the investigator’s judgment) are not to be recorded as adverse events. However, laboratory value changes that require treatment or adjustment in current therapy are considered adverse events. Where applicable, clinical sequelae (not the laboratory abnormality) are to be recorded as the adverse event.

The Investigator is expected to follow reported adverse events until stabilization or reversibility.

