3.5 Estimated Study Duration

3.5.1 Study Duration for Subjects

HeFH (rollover) subjects should enroll in Study 20120124 at the time of the week 24 (end of study [EOS]) visit in Study 20120123. For all subjects, after enrollment, the duration of study participation for a subject will be 80 weeks or approximately 18 ½ months.

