7. STUDY PROCEDURES

7.1 Schedule of Assessments

Approved

Table 2. Schedule of Assessments

Study Day / Week / Other Timepoint ^a	Screening		D1/Parent Study EOS	W4 ^c (±3d)	W12 (±7d)	W24 (±7d)	W36 (±7d)	W48 (±7d)	W60 (±7d)	W72 (±7d)	W80 (EOS) (±7d)
	HoFH	HeFH ^b									
General Procedures											
Informed parental/guardian consent/permission and subject consent/assent – HoFH subjects	X										
Informed parental/guardian consent/permission and subject consent/assent – HeFH subjects		X	X								
Enrollment			X ^d								
Medical history	X										
Vital Signs (sitting BP, HR)	X	X	X	X	X	X		X			X
Review for AEs/SAEs/ADEs	X ^e	X ^e	X	X	X	X	X	X	X	X	X
Concomitant therapy	X	X	X	X	X	X	X	X	X	X	X
Dietary instruction	X	X	X		X	X	X	X	X	X	
Physical exam (including neurologic examination)	X										X
Height, weight, cIMT, Tanner staging			X ^f			X		X			X
Neurocognitive assessment (Cogstate battery)	X		X ^g			X		X ^g			X
12 lead ECG			X								X
Central Laboratory^h											
Fasting lipids ^h	X	X ⁱ	X		X			X			X
ApoA1, ApoB100, Lp(a) ^h			X		X						X
PK (evolocumab), PCSK9			X		X						X
Chemistry, including fasting glucose ^h	X	X			X			X			X
Hematology	X	X						X			X
Estradiol (females) / testosterone (males)		X ⁱ	X								X
HbA1c, FSH, LH, ACTH, DHEA-S, cortisol, hsCRP, fasting vitamins A/D/E/K ^l		X ⁱ	X								X
CK	X	X ⁱ	X		X			X			X
Biomarkers (blood) ^k			X								X
Anti-evolocumab antibodies			X								X
HCV testing ^l	X										
HCV viral load ^l			X					X			X
Serum pregnancy ^m	X	X									X
Urine pregnancy ^m			X ^{n, o}	X	X	X	X	X	X	X	
Urinalysis, urine microalbumin, urine creatinine, urine albumin/creatinine ratio			X								X

Footnotes displayed on the next page of the Table

Approved

Table 2. Schedule of Assessments

Study Day / Week / Other Timepoint ^a	Screening		D1/Parent Study EOS	W4 ^c (±3d)	W12 (±7d)	W24 (±7d)	W36 (±7d)	W48 (±7d)	W60 (±7d)	W72 (±7d)	W80 (EOS) (±7d)
	HoFH	HeFH ^b									
Investigational Product											
Screening placebo AI/Pen (HoFH subjects only)	X										
IP administration on-site / instruction as needed			X	X	X	X	X	X	X	X	
AI/Pen or AMD dispensation ^p			X ^q	X	X	X	X	X	X	X	
AI/Pen or AMD reconciliation					X	X	X	X	X	X	X

Page 2 of 2

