7.7 Standardization of Study Procedures

7.7.1 Lipid Measurements

For subjects rolling over from Study 20120123, central laboratory results of the lipid panel, as well as ApoA1, ApoB, Lp(a), and PCSK9 will be unblinded when the subject has reached week 12 in Study 20120124. For these subjects, vitamins A, D, E, and K will also be blinded until the Study 20120123 database is locked. In addition, investigators and staff involved with this trial and all medical staff involved in the subject's medical care should refrain from obtaining lipid panels until week 12 in Study 20120124 and, if a lipid panel is drawn, all reasonable steps must be undertaken to avoid informing the subject and study personnel of the results.

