8.4 Detection of Bias

This study has been designed to minimize potential bias. For subjects rolling over from study 20120123, central laboratory results of the lipid panel, as well as ApoA1, ApoB, Lp(a), and PCSK9 will be blinded until the subject has reached week 12 in Study 20120124. For these subjects, vitamins A, D, E and K will also be blinded until the study 20120123 database is locked. In addition, investigators and staff involved with this trial and all medical staff involved in the subject's medical care should refrain from obtaining lipid panels until week 12 in Study 20120124 and, if a lipid panel is drawn, all reasonable

steps must be undertaken to avoid informing the subject and study personnel of the results.

Factors that may bias the results of the study include:

- Major protocol deviations likely to impact the analysis and interpretation of the efficacy endpoints

Important protocol deviations likely to impact the analysis and interpretation of the safety and efficacy endpoints will be tabulated in the Clinical Study Report (CSR).

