9.6.4 Laboratory Test Results

Descriptive statistics will be provided for actual values and changes from baseline in select laboratory parameters at select protocol-specified scheduled visit. Laboratory

analytes are provided in the protocol Table 3. CTCAE grading v5.0 or later will be used for lab shift table for liver function test (LFT).

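### The vitamin A/D/E/K blind for HeFH rollover subjects has no sample-date limit, so results drawn late in open-label treatment but before the parent-study lock are withheld from the investigator

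*Protocol*

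**What the plan says.** Protocol 7.7.1 (Lipid Measurements) sets two release rules for subjects rolling over from Study 20120123.

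- Lipid panel, ApoA1, ApoB, Lp(a) and PCSK9 results "will be unblinded when the subject has reached week 12 in Study 20120124".
- Vitamins follow a different rule: "For these subjects, vitamins A, D, E, and K will also be blinded until the Study 20120123 database is locked".

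SAP 8.4 (Detection of Bias) repeats the second rule: "For these subjects, vitamins A, D, E and K will also be blinded until the study 20120123 database is locked". Neither document limits it by visit or sample date, and neither gives an alert threshold, an unblinded reviewer or any other way for a markedly low vitamin result to reach the site.

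In protocol Table 2 (7.1) the vitamins sit in the row "HbA1c, FSH, LH, ACTH, DHEA-S, cortisol, hsCRP, fasting vitamins A/D/E/K". For HeFH subjects that row is scheduled at screening (only if the gap after the parent study exceeds 4 weeks), at Day 1 and at week 80. Week 80 is thus the only scheduled vitamin sample after Day 1. Protocol 7.2.2 adds that week-80 procedures should, if possible, be done when a subject withdraws early.

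On safety review, protocol 9.2.1.1 says: "The investigator is responsible for reviewing laboratory test results and determining whether an abnormal value in an individual study subject" is a clinically significant change from baseline. It does not exempt blinded analytes.

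**The concern.** The blind and the review duty are not reconciled. For any rollover vitamin sample drawn before the parent lock, the investigator is asked to judge laboratory results but does not receive this one.

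For samples at or just after Day 1 the blind has a clear purpose, because a vitamin value might hint at the parent-study arm. For samples taken late in open-label treatment that purpose has gone. Everyone in Study 20120124 is assigned open-label evolocumab. At week 80 the planned exposure is 80 weeks for a subject from the parent placebo arm and 24 + 80 = 104 weeks for one from the evolocumab arm. The direct markers of drug effect have by then been open to the site since week 12. The documents give no reason for holding vitamins longer.

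At stake is individual safety review in children: a low value without symptoms could go unassessed until after the subject has left the study. The rule covers rollovers only, so HoFH results are open and the two cohorts are reviewed differently.

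**Working it through.** The plan states no figure for this, so the check is one of timing: how many week-80 samples could fall before the parent lock?

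**Inputs from the documents**
- Rollover timing (protocol 3.5.1): "HeFH (rollover) subjects should enroll in Study 20120124 at the time of the week 24 (end of study [EOS]) visit in Study 20120123". Day 1 is therefore at parent week 24.
- Time to the last vitamin sample (protocol 3.5.1): "the duration of study participation for a subject will be 80 weeks or approximately 18 ½ months".
- Expected HeFH rollovers: about 111 (protocol 3.1).

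**Assumptions, because the documents do not give these**
- Parent entry time a is uniform over R weeks.
- The parent database is locked L weeks after the last parent visit. The main case is L = 8, with 4 to 26 as the range.
- There is no gap between the parent end-of-study visit and Day 1. A gap moves week 80 later and lowers the share.

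**Formula**
- Week-80 sample: a + 24 + 80 = a + 104.
- Lock: R + 24 + L.
- The sample is blinded when a + 104 < R + 24 + L, that is, a < R + L − 80.
- Share blinded = max(0, (R + L − 80)/R).
- Mean wait from sample to lock among those blinded = (R + L − 80)/2.

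**Results**

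| R (weeks) | Share, L = 4 | Share, L = 8 | Share, L = 26 | Of 111 at L = 8 | Mean wait at L = 8 |
|---|---|---|---|---|---|
| 52 | 0% | 0% | 0% | 0 | none |
| 78 | 2/78 = 3% | 6/78 = 8% | 24/78 = 31% | 9 | 3 weeks |
| 104 | 28/104 = 27% | 32/104 = 31% | 50/104 = 48% | 34 | 16 weeks |
| 156 | 80/156 = 51% | 84/156 = 54% | 102/156 = 65% | 60 | 42 weeks |

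No week-80 sample is affected unless R + L exceeds 80 weeks. The last subjects to roll over always reach week 80 after lock: 80 − L is 54 to 76 weeks after it for L between 26 and 4.

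**Early-withdrawal samples.** For a withdrawal at week w, 80 is replaced by w, and the share drawn before lock is (R + L − w)/R. With R = 52 and L = 8 this gives 36/52 = 69% at w = 24 and 12/52 = 23% at w = 48. Short accrual therefore clears the scheduled week-80 samples but not these. The documents do not give the number of such withdrawals.

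**Which accrual length is plausible?** The original protocol is dated May 2015, and Amendment 4 of May 2020 still revised the expected rollover number. SAP 5.3 also provides for subjects who have completed the study by the interim analysis, which is due once all have had the opportunity for 28 weeks of exposure. That allows for entry spread over more than 80 − 28 = 52 weeks. Both fit long accrual, but neither proves it, and neither dates the lock.

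**The case against.** The case against has real weight.

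- **The effect may be nil.** If the parent lock came before every late sample, the blind never touched one. This stands, which is why the size is given as a range starting at 0%.
- **Week 80 is the last visit.** A central-laboratory result from that draw would normally return after it, blinded or not. SAP 5.3 closes the treatment-emergent window for the primary analysis at the earlier of end of study and 30 days after the last dose. The blind therefore mainly lengthens a delay. This stands too, although a wait of weeks or months differs from ordinary laboratory turnaround.
- **Other routes exist.** Adverse events that are observed or reported are collected at every visit, and 9.2.1.1 prefers the clinical consequence to the laboratory finding as the recorded event. Only lipid panels are discouraged locally, so a local vitamin test is open. An external DMC reviews accumulating data, though its access to vitamin results is not stated.
- **Group summaries remain.** SAP 9.6.4 says "Descriptive statistics will be provided for actual values and changes from baseline in select laboratory parameters at select protocol-specified scheduled visit". The analyte table it refers to includes these vitamins, and SAP 9.1 summaries include minimum and quartiles. That gives a group picture at analysis but not a timely review of one child's result.
- **Release could harm the parent blind.** A withdrawal sample soon after Day 1 might still reflect the parent arm. This is correct, so release should not start at the first open-label dose.

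A reader might infer that a vitamin deficiency in a rollover subject cannot be recorded as an adverse event, and that the primary endpoint is therefore under-counted. The documents do not support that, given the routes above. Nor does 9.2.1.1 say that every single result must be reviewed; it states a general duty.

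**Conclusion.** The point holds in a limited form. The vitamin blind has no sample-date limit, and it conflicts with the laboratory-review duty for any post-Day-1 sample drawn before the parent lock. Once a subject has had a prolonged period of open-label treatment, withholding the result no longer protects the parent blind in any evident way. That is a judgement from the design, since the documents give no data on vitamin levels by arm.

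The share of week-80 samples affected runs from 0% with one year of parent accrual to 54% (about 60 of 111) with three years, if lock is 8 weeks after the last parent visit, accrual is uniform and there is no rollover gap. Later early-withdrawal samples can be affected even with short accrual.

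It would be tempting to say that all HeFH week-80 vitamin results are hidden, or that every subject is on evolocumab at that visit. Neither follows. Late rollovers' results are open, and subjects who stop the drug are still asked to attend. What can be lost is an asymptomatic low value that the investigator would have judged clinically significant. No effect on the primary endpoint can be quantified from the documents. The gap is modest but cheap to close.

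**What to change.** In protocol 7.7.1 and SAP 8.4, limit the vitamin blind for rollover subjects to samples drawn before week 12 of Study 20120124, the point at which lipids and PCSK9 are released. Release vitamin results from samples drawn at or after week 12 to the investigator, including week 80 and early-withdrawal samples from that point on. Keep parent-study, Day 1 and other pre-week-12 results blinded until the parent lock.

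The cost is one sentence in each document and a changed reporting setting at the central laboratory, with no new samples or visits. One limit remains. SAP 5.2 takes the parent-study value as baseline for rollovers, and that value stays blinded. Until lock the investigator can therefore judge the on-study value itself but cannot fully judge change from baseline. The text should say that this comparison is completed once the baseline is released. If the parent database was already locked before any sample at or after week 12 was drawn, the edit has no practical effect, and a note giving the lock date would be enough.
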